4.2 INCLUSION CRITERIA

Potential subjects must satisfy all of the following criteria to be enrolled in the study:

Subjects should meet all study Inclusion Criteria as outlined below:

1. The subject must read and sign the Informed Consent form.
2. The subject must appear able and willing to adhere to the instructions set forth in this clinical protocol.
3. Healthy adult males or females age ≥ 18 years of age with signed informed consent. Eligible presbyopes will be those that wear full distance contact lenses in both eyes, then wear reading glasses over them.
4. The subject's optimal vertexed spherical equivalent distance correction must be between -1.00 and -6.00D.
5. The subject's refractive cylinder must be ≤ 1.00 D in each eye.
6. The subject must have visual acuity best correctable to 20/25+3 or better for each eye.
7. Subjects should own a wearable pair of spectacles.
8. The subject is a current spherical soft contact lens wearer (defined as a minimum of 6 hours of DW per day, at least 5 days per week, for a minimum of 1 month prior to the study) and willing to wear the study lenses on a similar basis.
9. Subjects must be able and willing to wear the study lenses at least 6 hours a day, a minimum of 5 days per week
10. The subject must have normal eyes (i.e., no ocular medications or infections of any type).

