4.3 EXCLUSION CRITERIA

Potential subjects who meet any of the following criteria will be excluded from participating in the study:

1. Currently pregnant or lactating (subjects who become pregnant during the study will be discontinued).
2. Any systemic disease, autoimmune disease, or use of medication, which may interfere with contact lens wear. This may include, but not be limited to, diabetes, hyperthyroidism, recurrent herpes simplex/zoster, Sjögren's syndrome, xerophthalmia, acne rosacea, Stevens-Johnson syndrome, and immunosuppressive diseases or any infectious diseases (e.g. hepatitis, tuberculosis).
3. Use of any of the following medications within 1 week prior to enrollment: oral retinoid isotretinoin (e.g. Accutane), oral tetracyclines, topical scopolamine, oral (e.g. Seldane, Chlor-Trimeton, and Benadryl) and ophthalmic antihistamines, oral phenothiazines (e.g., Haldol, Mellaril, Thorazine, Elavil, Pamelor, Compazine), oral and ophthalmic Beta-adrenergic blockers (e.g., Propranolol, Timolol, and Practolol), systemic steroids, and any prescribed or over the counter (OTC) ocular medication.
4. Entropion, ectropion, extrusions, chalazia, recurrent styes, glaucoma, history of recurrent corneal erosions, aphakia, or moderate or above corneal distortion by keratometry.
5. Any previous, or planned, ocular or interocular surgery (e.g., radial keratotomy, PRK, LASIK, etc.).

6. Any grade 2 or greater slit lamp findings (e.g., edema, corneal neovascularization, corneal staining, tarsal abnormalities, conjunctival injection) on the FDA classification scale, any previous history or signs of a contact lens-related corneal inflammatory event (e.g., past peripheral ulcer or round peripheral scar), or any other ocular abnormality that may contraindicate contact lens wear.
7. Any known hypersensitivity or allergic reaction to Optifree®Puremoist® multi-purpose care solution or Eye-Cept® rewetting drop solution
8. Any ocular infection, allergy or clinically significant ocular disease (e.g. corneal edema, uveitis, severe keratoconjunctivitis sicca, ocular hypertension), or ocular conditions (e.g. strabismus), which might interfere with the study.
9. Any corneal distortion resulting from previous hard or rigid gas permeable contact lens wear.
10. Toric, extended wear, monovision or multi-focal contact lens correction.
11. Participation in any contact lens or lens care product clinical trial within 30 days prior to study enrollment.

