4	14-days (± 2 days) from visit 3. Third follow-up for the test lens, subjective responses, VA, fitting characteristics, surface characteristics, physiology. Four new lenses of the same power and type will be dispensed for approximately 4 weeks (biweekly replacement).	1.5 hours
5	28-days (± 4 days) from visit 4. Fourth follow-up for the test lens, subjective responses, VA, fitting characteristics, surface characteristics, physiology. Four new lenses of the same power and type will be dispensed for approximately 4 weeks (biweekly replacement).	1.5 hours
6	28-days (± 4 days) from visit 5. Fifth follow-up for the test lens, subjective responses, VA, fitting characteristics, surface characteristics, physiology. Subjects will be placed back into their habitual lenses.	1.5 hours
7	7-days (± 1 days) from visit 6. First follow-up for the habitual lens, subjective responses including preferences , VA, fitting characteristics, surface characteristics, physiology. Same habitual lens type to be worn approximately one more week.	1.5 hours
8	7-days (± 1 days) from visit 7. Second follow-up for the habitual lens, subjective responses, VA, fitting characteristics, surface characteristics, physiology. Final Evaluation.	1.0 hours

[figure not shown]

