4.6 WEAR AND REPLACEMENT SCHEDULES, INCLUDING FORM, PACKAGING AND LABELING

Wear Schedule: Daily wear

Replacement Schedule: 2 week

Test Article Packaging Description: Blister packaging in sterile packing solution

Labeling: Investigational

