15	Lens Deposits	Record the front and back surface deposits of the lenses.	
16	Lens Wettability	Record the white light lens wettability of both lenses.	

VISIT 2: 7-DAY FOLLOW-UP

(Follow-up #1, 6-8 days after Visit 1)

The following information will be collected:

Steps		Details	
17	Lens Damage	Lens damage (draw in source document and describe). Replace lens if damaged and complete the Product Quality Complaint form and save lens in vial with Optifree PureMoist or saline.	
18	Temporary Lens Removal & Storage	The lenses will be removed and temporarily stored in suitable lens case with Opti-Free PureMoist or saline. The lenses should not be rubbed and will be reinserted in step 21.	
19	Slit Lamp Findings	Slit Lamp Classification Scale [REDACTED] will be used to grade the findings. Record only whole numbers. Note: Subject must be free of any FDA grade 3 or greater slit lamp findings with no active ocular infection/inflammation.	
20	Eye Rinse	The study coordinator, investigator, or technician will rinse the subject's eyes thoroughly with saline.	
21	Lens Re-Insertion	The same lenses removed in step 18 will be placed back on the eyes and worn for an additional 6-8 days.	
22	Exit Visual Acuity	Record the distance Snellen visual acuity with the study lenses (OD, OS, and OU) to the nearest letter. Smaller lines must be shown until the subject incorrectly identifies at least 50% of the letters.	
23	Follow-up Visit Scheduling	An appointment for the next visit should be made for approximately 7 days (range 6-8 days) after Visit 2. Subjects should be advised to wear the study lenses at least 6 hours a day, and a minimum of 5 days per week. The study lenses must be worn into the Follow-up Visit.	

VISIT 3: 14-DAY FOLLOW-UP

(Follow-up #2, 6-8 days after Visit 2)

The following information will be collected:

Steps		Details	
1	Concomitant Medications and Medical History Review	Record the concomitant medications and review the subject's medical history, specifically noting any changes from baseline.	
2	Wearing Time	Record the average wearing time and comfortable wearing time.	
3	Compliance	Confirm compliance with the prescribed wear schedule, including adherence to the rub regime.	

VISIT 3: 14-DAY FOLLOW-UP

(Follow-up #2, 6-8 days after Visit 2)

The following information will be collected:

Steps		Details	
4	Use of Lens Rewetting Drops	The subjects will record the approximate daily use of lens rewetting drops (i.e., how many times per day on average).	

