6	Lens Fit Assessment:	
The fit of the lens is judged by the investigator as pass or fail based on the criteria below. If the fit of the lens is judged as a failure, the subject is terminated from the study. To be judged as a failure, the lens must display one or more of the following:
 
 1. Limbal exposure in any gaze 2. Edge lift 3. Insufficient and/or excessive movement in all three movement categories 	█ █
7	Lens Deposits	Record the front and back surface deposits of the lenses.	█
8	Lens Wettability	Record the white light lens wettability of both lenses.	█

VISIT 6: HABITUAL LENS RELEASE #1**(24-32 days after Visit 5)****The following information will be collected:**

Steps		Details	
1	Habitual Lens Release	
The subject's habitual lenses will be worn for 6-8 days.
 
 1. The subjects should wear their lenses similar to the inclusion criteria: ≥ 6 hours per day, ≥ 5 days per week. 2. The lenses will be worn as daily wear only. 3. All subjects will be provided Opti-Free PureMoist to be used in a rub regime. 4. Preservative-free rewetting drops are permitted if needed. 
Note: Daily disposable wearers do not need to adhere to the Optifree PureMoist solution and rub regime.
	█
2	Follow-up Visit Scheduling	An appointment for the next visit should be made for approximately 7 days (range 6-8 days) after Visit 6. Subjects should be advised to wear their habitual lenses at least 6 hours a day, and a minimum of 5 days per week. Their habitual lenses must be worn into the Follow-up Visit.	

VISIT 7: 7-DAY FOLLOW-UP HABITUAL LENS

(Follow-up #1, 6-8 days after Visit 6)

The following information will be collected:

Steps		Details	
1	Concomitant Medications and Medical History Review	Record the concomitant medications and review the subject's medical history, specifically noting any changes from baseline.	
2	Wearing Time	Record the average wearing time and comfortable wearing time.	
3	Compliance	Confirm compliance with the prescribed wear schedule, including adherence to the rub regime.	
4	Use of Lens Rewetting Drops	The subjects will record the approximate daily use of lens rewetting drops (i.e., how many times per day on average).	
5	Subject-reported Ocular Symptoms	The subject will respond to a Symptoms Questionnaire.	
6	Glare Questionnaire	The subject will respond to the Eyestrain Caused by Glare Questionnaire in regards to their habitual lenses.	

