7	Project-Specific Questionnaire	The subject will respond to the Project-Specific Questionnaire	
8	CLUE Follow-up Questionnaire	The subject will respond to the CLUE Follow-up Questionnaire	
9	Patient Reported Outcomes	Subjects will respond to the following individual questions. 1. Subjective Comfort (Item ID: ISOC0001) 2. Subjective Vision (Item ID: ISOV0001) 3. Subjective Handling (Item ID: ISOH0001)	
10	Lens Preferences	Subjects will respond to preference questions relating back to their habitual lenses.	
11	GSI Product Performance Questionnaire	Subjects will respond to the GSI Product Performance Questionnaire.	
12	Entrance Visual Acuity	Record the distance visual acuity with the habitual contact lenses (OD, OS, and OU) to the nearest letter. Smaller lines must be shown until the subject incorrectly identifies at least 50% of the letters.	

The following information will be collected:

Steps		Details	
13	Spherical Over-refraction	Perform a spherical over-refraction OD and OS using any acceptable means (i.e., phoropter, trial lenses, flipper bars) in normal room illumination and record the resultant distance Snellen visual acuity OD and OS.	
14	Lens Fit Assessment:	Subjective Assessment of the Lens Fit. If the fit is graded as unacceptable based on the criteria below, then the subject is discontinued from the study and will not be replaced. 1. Limbal exposure in any gaze 2. Edge lift 3. Insufficient and/or excessive movement in all three movement categories	
15	Lens Deposits	Record the front and back surface deposits of the lenses.	
16	Lens Wettability	Record the white light lens wettability of both lenses.	
17	Temporary Lens Removal & Storage	The lenses will be removed and temporarily stored in suitable lens case with Opti-Free PureMoist or saline. The lenses will be reinserted in step 20.	
18	Slit Lamp Findings	Slit Lamp Classification Scale [REDACTED] will be used to grade the findings. Record only whole numbers. Note: Subject must be free of any FDA grade 3 or greater slit lamp findings with no active ocular infection/inflammation.	
19	Eye Rinse	The study coordinator, investigator, or technician will rinse the subject's eyes thoroughly with saline.	
20	Lens Re-Insertion	The same lenses removed in step 17 will be placed back on the eyes and worn for an additional 6-8 days.	

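### Visit 7 steps 17 and 20 send every subject home in the same pair of habitual lenses for 6 to 8 more days, which is wrong for daily disposable wearers

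*Protocol*

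**What the plan says.** After 12 weeks in study lenses, subjects return to their own lenses at Visit 6 and are seen again at Visits 7 and 8.

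At Visit 7, step 17 has the habitual lenses taken out and kept in a case with multipurpose solution or saline, and adds: "The lenses will be reinserted in step 20". After the slit lamp examination and eye rinse, step 20 reads: "The same lenses removed in step 17 will be placed back on the eyes and worn for an additional 6-8 days". Neither step depends on the kind of lens the subject wears.

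The Visit 6 release step, which opens the habitual-lens phase, does make a distinction: "Daily disposable wearers do not need to adhere to the Optifree PureMoist solution and rub regime".

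On who may enrol, inclusion criterion 8 states "The subject is a current spherical soft contact lens wearer" and adds a minimum wearing time. Exclusion criterion 10 removes "Toric, extended wear, monovision or multi-focal contact lens correction". Daily disposable lenses are not listed there.

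The Visit 7 row of the visit table in section 4.4 is looser than step 20: "Same habitual lens type to be worn approximately one more week".

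**The concern.** A daily disposable lens is meant for one day. Step 20 identifies the lenses by their removal in step 17, so it points to a physical pair and not to a brand or type. For a daily disposable wearer that is the wrong instruction. It comes one visit after the protocol has recognised this group and waived its lens care.

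Two things are at stake, both modest. A site that follows step 20 literally has a single-use pair re-worn for about a week while the cleaning regime is waived, which is an avoidable risk to the subject. A site that uses a fresh pair does the right thing but departs from the written procedure, and SAP section 4.4 has all reported deviations listed. Symptoms, glare responses and slit lamp findings are still collected at Visit 8, so the lens actually worn between Visits 7 and 8 should be unambiguous.

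**Working it through.** The plan gives no figure on this point, so the check is a comparison of texts.

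1. **Can daily disposable wearers be in the study?** Yes. Inclusion criterion 8 admits any current spherical soft lens wearer who meets the wear-time rule, and exclusion criterion 10 names four other kinds of correction. The Visit 6 note would have no purpose if such wearers could not enrol.

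2. **What does Visit 6 change for them?** Only the solution and rub regime. No step in Visits 6 to 8 tells them to open a fresh pair.

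3. **What does Visit 7 then require?** Storage and reinsertion of the removed pair, followed by 6 to 8 days of wear. For a single-use lens the contrast is 6 to 8 days on one pair against one day per pair.

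4. **Where does the wording probably come from?** Visit 2 step 21 reads: "The same lenses removed in step 18 will be placed back on the eyes and worn for an additional 6-8 days". Apart from the step number it is the same sentence. At Visit 2 it is correct, because the lenses are study lenses and section 4.6 sets "Replacement Schedule: 2 week". One week into a two-week lens, reinsertion is what is wanted. At Visit 7 the lenses are the subject's own and may be single-use. That the sentence was carried over is an inference from the matching text; the documents do not say so.

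5. **Does section 4.4 contradict step 20?** No. Wearing the same type for another week is satisfied both by re-wearing one pair and by using fresh pairs. Step 20 is narrower, and it is the numbered instruction that a site carries out.

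6. **Does any planned comparison use these data?** The primary and secondary models stop at week 12, which is Visit 6, and SAP section 1.1 limits the SAP to that period. Visit 7 comes afterwards, so no estimate, alpha level or power figure depends on step 20.

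7. **How many subjects?** The documents do not say. Visit 1 screening step 4 records the name and wearing modality of each subject's habitual lens, so the sponsor should be able to count them from data already collected.

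**The case against.** The best reply is that the protocol, read as a whole, makes its meaning plain. The Visit 6 release step also speaks of habitual lenses worn for 6 to 8 days, with the daily disposable note directly beneath it, so there the phrase must describe a period in a lens type. Step 20 can be read as continuing that period. Waiving lens care makes sense only if these subjects replace lenses daily. Section 4.4 refers to lens type, and Visit 7 step 22 refers simply to the subject's habitual lenses. The subjects are experienced wearers seen by eye care professionals. All of this stands, and it makes harm unlikely. It does not alter step 20, which, unlike the Visit 6 sentence, ties the lenses to those just removed.

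A second reply is that there may be nobody to whom this applies. SAP section 1.3 says that enrolled subjects must be habitual wearers of frequent replacement silicone hydrogel lenses. That is fair evidence that the number could be small or zero. It does not set eligibility: SAP section 1.1 gives the SAP precedence only over protocol section 9, and the protocol's own criteria contain no such limit.

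A reader might also infer that the package insert in section 16.4 settles the matter, since its lens care directions say that disposable lenses are discarded on removal. The documents do not support that much. The insert covers the control product, not a subject's own lens. It also mentions disposable wear under indications, leaves the replacement schedule for disposable wear to the eye care professional, and allows emergency cleaning when no replacement or spectacles are at hand. The point rests on the mismatch between Visit 6 and Visit 7, not on the insert.

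**Conclusion.** The point holds as a minor wording error. Visit 7 steps 17 and 20 give an instruction that is wrong for a group the protocol admits and expects. Confidence is high about the text and lower about the consequence, because the intent is fairly clear and many sites would act on it. The size is unknown: no count of daily disposable wearers is given, and it may be zero.

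Two stronger readings should be resisted. A reader might infer that the efficacy or safety comparison is compromised; it is not, since the planned analyses end at week 12, before this step. A reader might also infer that a deviation logged at Visit 7 would remove the subject from the per-protocol set. Protocol section 9.1 and SAP section 2.2.1 exclude only substantial deviations, as judged by the cohort review committee before hard lock, and nothing suggests that a fresh pair of the subject's own lens would count as one.

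**What to change.** Reword Visit 7 steps 17 and 20 in two branches:

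- Wearers of reusable lenses store the removed pair and reinsert it, as now.
- Daily disposable wearers discard the removed pair, insert a fresh pair of the same habitual type and power, and replace lenses daily until Visit 8.

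At Visit 6, when the next appointment is made, remind daily disposable wearers to bring a spare pair. Visit 5 Dispensing #4, Note 4 already does this for habitual lenses in general. Give a fallback: a subject who brings no spare leaves in spectacles, which inclusion criterion 7 says subjects should own, and resumes lens wear with a fresh pair.

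Record that for these subjects the exit acuity at Visit 7 step 21 is on a fresh pair, or is not done if there is no spare. This is a small loss, because entrance acuity (step 12) and exit acuity would no longer refer to the same lenses. Neither measurement enters a primary or secondary analysis.

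The cost is wording in two steps, one reminder and one recording note, with no added visits, subjects or analyses.

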4.8 DISCONTINUATION CRITERIA

Johnson & Johnson Vision Care, Inc. reserves the right to terminate the study at any time for any reason. Additionally, the IRB/IEC reserves the right to terminate the study if an unreasonable risk is determined. The study may be terminated by the Principal Investigator or Medical Monitor due to specific clinical observations, if in their opinion it would be unwise to continue.

Johnson & Johnson Vision Care, Inc. [*and the IRB/IEC, if applicable*] will evaluate all adverse events. If it is determined that an adverse event presents an unreasonable risk, the investigation, or that part of the investigation presenting the risk, will be terminated, as soon as possible.

Should the study be terminated (either prematurely or as scheduled), the Investigator will notify the Institutional Review Board (IRB), and Regulatory Authority as required by local regulatory requirements.

4.9 ACCOUNTABILITY PROCEDURES FOR STUDY ARTICLES

Johnson & Johnson Vision Care, Inc. will provide the Investigator with sufficient quantities of study articles and supplies to complete the investigation. The Investigator is asked to retain all lens shipment documentation for the test article accountability records. The Investigator may provide the subject additional lenses when a lens is damaged or lost between visits. Subjects must return to the investigational site for a replacement lens.

Test articles must be kept in a locked storage cabinet, accessible only to those assigned by the Investigator for dispensing. All investigational products must be accounted. This includes 1) what was dispensed for the subject to wear out of the office or issued for the subject to replace appropriately between visits, 2) what was returned to the Investigator unused, and 3) the number and reason for unplanned replacements. The Investigator may delegate this activity to an authorized study site staff member on the Delegation Log.

The Investigator will collect all unused test articles from the subjects at the end of the subject's participation. Following final reconciliation of test articles, the Investigator will package and return all unused study articles to JVCI.

Please reference APPENDIX C: TEST ARTICLE ACCOUNTABILITY IN THE EDC SYSTEM for instructions on the Lens Depot.

The following table summarizes all documentation of receipt, usage, and return.

	Documentation	Description
Prior to Study Beginning	Test Article Shipped Form / Order Receipt Record	Confirms shipment contents. Two representatives from the site must sign the TAS form accepting and confirming the quantity and condition of the Test Articles received. If a discrepancy exists, contact the Sponsor immediately to launch an investigation. If warranted, a corrected TAS form will be sent to the site. The original TAS form will be maintained at the site in the study files, a copy confirming receipt will be sent back to the Sponsor.
	EDC Lens Depot / Receiving Test Articles in the EDC.	Confirms shipment contents in the EDC. Must be completed prior to dispensing. A site representative will log into the EDC accepting receipt of each Test Article lot. If a discrepancy exists, contact the Sponsor immediately to launch an investigation, only accept the quantity that is physically in the shipment. Refer to Appendix C for complete instructions on how to Receive, Dispense, and Return Test Articles in the EDC.
During Study Dispensing	Contact Lens Dispensing Log	Accounts for all test articles issued, used and returned by each study subject, as well as any unplanned replacements
	Subject Record	Test article distribution information in the subject record must correspond with the Lens Accountability Log and the corresponding CRF
Study Conclusion/ Close-Out	Return Sheet	Requested by the Site, during Study Conclusion/Close-Out. Accompanies unused product for return to Sponsor. The Sponsor Monitor must sign the Return Sheet Prior to the Site shipping the Test Articles to JVICI. The original Return Sheet will be maintained at the site in the study files, a copy confirming receipt will be sent back to the Sponsor.
	EDC Lens Depot / Returning Test Articles in the EDC.	Confirms return shipment contents back to JVICI in the EDC. Must be completed prior to shipping Test Articles back to JVICI. A site representative will log into the EDC, entering in the return amount of each Test Article lot. Refer to Appendix C for complete instructions on how to Receive, Dispense, and Return Test Articles in the EDC.
	Lens Reconciliation	The monitor will review all the lens accountability records and attempt to reconcile. Explanation will be needed for any unaccounted test articles.

Note: If there is a discrepancy between the shipment sheet and contents, contact the study monitor immediately.

